10.1.2.2.2 Reporting of Pregnancies Occurring During the Study

Study site personnel must report every pregnancy from the time the subject signs the ICF until 30 days after receiving the last dose of study drug. Within 24 hours of learning of the pregnancy, the study site personnel must report the event to the sponsor's Global Patient Safety department on the Clinical Trial Pregnancy Form and fax/email it to the following SAE/pregnancy fax number/email address, even if no AE has occurred:

[contact] (back-up [contact])
Email: [contact]

Pregnancies in female partners of male subjects occurring during the time frame described above must also be reported.

The pregnancy must be followed to term and the outcome reported by completing a follow-up Clinical Trial Pregnancy Form. If the pregnancy is associated with an SAE (eg, if the mother is hospitalized for hemorrhage), a separate SAE Form for Clinical Trials must be filed with the appropriate serious criterion (eg, hospitalization) indicated in addition to the Clinical Trial Pregnancy Form.

10.1.2.2.3 Unexpected Adverse Reactions

Unexpected Adverse Reaction Definition

An unexpected adverse reaction is any untoward and unintended response that is related to the administration of the study drug at any dose that is not consistent with the applicable product information (eg, investigators brochure for an unauthorized investigational medicinal product or summary of product characteristics for an authorized product).

CONFIDENTIAL

All suspected unexpected serious adverse reactions (SUSARs) will be the subject of expedited reporting. The sponsor shall ensure that all relevant information about a SUSAR that is fatal or life-threatening is reported to the relevant competent authorities and institutional review board (IRB) within 7 days after knowledge by the sponsor of such a case and that relevant follow-up information is communicated within an additional 8 days. All other SUSARs will be reported to the relevant competent authorities and IRB within 15 days after knowledge by the sponsor of such a case. All investigators should follow up SUSARs until the event is resolved or until, in the opinion of the investigator, the event is stabilized or determined to be chronic. Post study SUSARs that occur after the subject has completed the clinical study must be reported by the investigator to the sponsor.

10.1.2.2.4 Warnings and Precautions

Clinical Worsening/Suicide Risk: subjects should be monitored for clinical worsening, suicidality and unusual change in behavior, especially at the start of therapy or at times of dose changes. (See [Section 10.1.2.1](#) for use of the C-SSRS).

Serotonin Syndrome: serotonin syndrome has been reported with SSRIs, including escitalopram, when taken alone, but especially when co-administered with other serotonergic agents (including triptans, tricyclic antidepressants, fentanyl, lithium, tramadol, tryptophan, buspirone, amphetamines, and St. John's Wort). Serotonin syndrome symptoms may include mental status changes (eg, agitation, hallucinations, delirium, and coma), autonomic instability (eg, tachycardia, labile blood pressure, dizziness, diaphoresis, flushing, and hyperthermia), neuromuscular symptoms (eg, tremor, rigidity, myoclonus, hyperreflexia, and incoordination) seizures, and/or gastrointestinal symptoms (eg, nausea, vomiting, and diarrhea). If symptoms of serotonin syndrome occur, escitalopram should be discontinued and supportive treatment initiated.

Hyponatremia: hyponatremia may occur as a result of treatment with SSRIs, including escitalopram. Subjects taking diuretics or who are otherwise volume depleted may be at greater risk. Discontinuation of escitalopram should be considered in subjects with symptomatic hyponatremia and appropriate medical intervention should be instituted.

Caution should be used when escitalopram is taken in combination with other centrally acting drugs.

Full details of the Warnings and Precautions associated with escitalopram are available in the prescribing information.

10.1.2.2.5 Overdose

Symptoms most often accompanying escitalopram overdose, alone or in combination with other drugs and/or alcohol, include convulsions, coma, dizziness, hypotension,

CONFIDENTIAL

insomnia, nausea, vomiting, sinus tachycardia, somnolence, and ECG changes (including QT prolongation and very rare cases of torsade de pointes). Acute renal failure has been very rarely reported accompanying overdose.

In managing overdosage, consider the possibility of multiple-drug involvement. The physician should consider contacting a poison control center for additional information on the treatment of any overdose.

10.1.2.2.6 Potential Hy's Law Cases

Criteria for potential Hy's law cases are as follows:

- Alanine aminotransferase (ALT) or aspartate aminotransferase (AST) $\geq 3 \times$ upper limit of normal (ULN) AND
- Total bilirubin $\geq 2 \times$ ULN AND
- Alkaline phosphatase $< 2 \times$ ULN

Study site personnel must report every subject who meets these criteria. Typically, all 3 analytes will be obtained from the same sample, but they may come from multiple samples taken within a 24-hour period. This requirement applies from the time the subject signs the ICF for the study until 30 days after receiving the last dose of study drug.

A laboratory alert for potential Hy's law cases will be in place, and the laboratory must notify investigators and the sponsor immediately when the above criteria have been met. A potential Hy's law case must be reported to the sponsor on an SAE form as soon as possible (within 24 hours of learning of the potential Hy's law case) to the SAE/pregnancy fax number, even if no AE has occurred. The eCRF for potential Hy's law cases must be completed within 7 calendar days. Every effort to determine the cause of the liver enzyme abnormalities must be made, and close monitoring should be initiated in conjunction with the Study Medical Monitor and in accordance with the FDA Guidance for Industry, Drug-Induced Liver Injury: Premarketing Clinical Evaluation, July 2009. The patient should return to the study site and be evaluated as soon as possible, preferably within 48 hours from the time the investigator becomes aware of the abnormal results. This evaluation should include laboratory tests, detailed history, and physical examination.

10.1.2.3 Clinical Laboratory Evaluation

The hematology, clinical chemistry, urinalysis, and other laboratory variables analyses (see [Section 10.1.2.3.1](#)) will be performed at a central laboratory. Reference ranges will be used by the investigator to assess the laboratory data for clinical significance and pathological changes. The following laboratory safety tests will be performed at the times outlined in the Schedule of Assessments in [Section 8.1.2](#). Information on

CONFIDENTIAL

collection, processing, and shipping of samples will be provided in the Laboratory Manual.

Hematology

Hemoglobin, hematocrit, white blood cell count (total and differential), red blood cell count, platelet count, mean cell volume, mean cell hemoglobin (MCH), and MCH concentration.

Clinical Chemistry

Creatinine, urea (or blood urea nitrogen), aspartate transferase, alanine transferase, gamma glutamyltransferase, alkaline phosphatase, lactate dehydrogenase, total bilirubin, albumin, total protein, sodium, potassium, chloride, glucose, uric acid, calcium, phosphorus, TSH, T3, and T4.

Urinalysis

pH, glucose, ketones, blood, protein, and microscopy.

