11.6.1.4 Clinical Laboratory Evaluations

Descriptive statistics for clinical laboratory values (in SI units) and changes from the baseline values at each assessment time point will be presented by treatment group for each clinical laboratory parameter. The number and percentage of subjects with PCS postbaseline clinical laboratory values will be tabulated by treatment group. The criteria for PCS laboratory values will be detailed in the SAP. The percentages will be calculated relative to the number of subjects with available non-PCS baseline values and at least one postbaseline assessment. The numerator will be the total number of subjects with available non-PCS baseline values and at least one PCS postbaseline value. A supportive listing of subjects with PCS postbaseline values will be provided, including the SID number, study center number, and baseline and postbaseline values. A listing of all AEs for subjects with PCS laboratory values will also be provided.

CONFIDENTIAL

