10.2 CLINICAL LABORATORY PARAMETERS

Descriptive statistics for clinical laboratory values (in SI units) and changes from the baseline values at each assessment time point (including the end of the double-blind acute treatment period) will be presented by treatment group for the following laboratory parameters:

Hematology: Hemoglobin, hematocrit, white blood cell count (total and

differential), red blood cell count, platelet count, mean cell volume, mean cell hemoglobin (MCH), and MCH concentration.

Chemistry: Creatinine, urea (or blood urea nitrogen), aspartate transferase,

alanine transferase, gamma glutamyltransferase, alkaline phosphatase, lactate dehydrogenase, total bilirubin, albumin, total protein, sodium, potassium, chloride, glucose, uric acid, calcium,

phosphorus, thyroid-stimulating hormone, T3, and T4.

Urinalysis: pH, glucose, ketones, blood, protein, and microscopy.

Clinical laboratory test values will be considered potentially clinically significant (PCS) if they meet either the lower-limit or higher-limit PCS criteria listed in Table 10.2–1. The number and percentage of subjects who have PCS post-baseline clinical laboratory values will be tabulated by treatment group. The percentages will be calculated relative to the number of subjects with available non-PCS baseline values and at least 1 postbaseline assessment. The numerator will be the total number of subjects with available non-PCS baseline values and at least 1 PCS post-baseline value. A supportive listing of subjects with PCS post-baseline values will be provided, including the subject identification (SID) number, study center number, and baseline and all post-baseline (including non-PCS) values.

In addition, a listing of all AEs that occurred in subjects who had PCS post-baseline clinical laboratory values will be provided.

Table 10.2–1. Criteria for Potentially Clinically Significant Laboratory Values

Parameter	SI Unit	Lower Limit	Higher Limit
HEMATOLOGY			
Basophils	%		> 6
Eosinophils	%		> 10
Hematocrit	1.0	< 0.9 × LLN	
Hemoglobin	g/L	< 0.9 × LLN	
Lymphocytes	%	< 10	> 60
Monocytes	%	_	> 20
Neutrophils	%	< 30	> 90
Platelet count	× 10 ⁹ /L	≤ 75	≥ 700

Page 33 of 53

White blood cell count	$\times 10^9/L$	≤ 2.5	≥ 15
CHEMISTRY			
Albumin	g/L	< 0.9 × LLN	> 1.1 × ULN
Alkaline phosphatase	U/L	_	\geq 3 × ULN
Alanine	U/L		\geq 3 × ULN
aminotransferase	U/L	_	≥ 3 ^ OLN
Aspartate	U/L		\geq 3 × ULN
aminotransferase			_
Bicarbonate	mmol/L	< 0.9 × LLN	> 1.1 × ULN

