Blood urea nitrogen	mmol/L		> 1.2 × ULN
Calcium	mmol/L	< 0.9 × LLN	> 1.1 × ULN
Chloride	mmol/L	< 0.9 × LLN	> 1.1 × ULN
Cholesterol, total	mmol/L	_	> 200mg/dL
Creatinine	μmol/L	_	> 1.3 × ULN
Glucose	mmol/L	< 0.8 × LLN	> 1.4 × ULN
high-density		< 40 m ~/4I	
lipoprotein	mmol/L	< 40 mg/dL	_
Low-density lipoprotein	mmol/L	_	> 130 mg/dL
Magnesium	mmol/L	< 0.9 × LLN	> 1.1 × ULN
Phosphate	mmol/L	< 0.9 × LLN	> 1.1 × ULN
Potassium	mmol/L	< 1.0 × LLN	> 1.0 × ULN
Sodium	mmol/L	< 1.0 × LLN	> 1.0 × ULN
Total bilirubin	μmol/L	_	> 1.5 × ULN
Total protein	g/L	< 0.9 × LLN	> 1.1 × ULN
Triglyogrido	mmol/L		> 100 mg/dL (ages 7-10),
Triglyceride	IIIIIIOI/L		>130 mg/dL (ages 11-17)
URINALYSIS			
Protein	g/L		at least two +
Glucose	mmol/L	_	at least two +

LLN = lower limit of normal value provided by the laboratory; SI = Le Système International d'Unités (International System of Units); ULN = upper limit of normal value provided by the laboratory.

Shift tables from baseline to the end of double-blind acute treatment period for clinical laboratory parameters will be presented by treatment group for the following categories: low, normal, and high.

Potential Hy's Law criteria is defined by a postbaseline elevation of alanine aminotransferase (ALT) or aspartate aminotransferase (AST) \geq 3× ULN (ULN = upper limit of normal laboratory reference range), along with total bilirubin (TBL) \geq 2× ULN and a non-elevated alkaline phosphatase (ALP) < 2× ULN, all based on blood draws collected within a 24-hour period. The number and percentage of subjects who meet the following criteria of clinical interest during the double-blind acute treatment period will be tabulated by treatment group. A supportive list will also be provided.

• ALT: $\geq 3 \times$ ULN, $\geq 5 \times$ ULN, $\geq 10 \times$ ULN, $\geq 20 \times$ ULN

Page 34 of 53

- AST: $\geq 3 \times ULN$, $\geq 5 \times ULN$, $\geq 10 \times ULN$, $\geq 20 \times ULN$
- ALT or AST: $\geq 3 \times$ ULN, $\geq 5 \times$ ULN, $\geq 10 \times$ ULN, $\geq 20 \times$ ULN
- TBL: > 1.5 x ULN. 2 × ULN
- ALP: $< 2 \times ULN$
- Concurrent elevations:
 - ALT or AST \geq 3× ULN with TBL \geq 1.5× ULN;
 - ALT or AST \geq 3× ULN with TBL \geq 2× ULN;
 - ALT or AST \geq 3× ULN with TBL \geq 2× ULN and ALP < 2× ULN.

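### The chemistry limits in SAP Table 10.2–1 do not fit the trial's listed panel: six of its 20 rows match no listed analyte, and six of the 20 listed analytes, including TSH, T3 and T4, have no PCS limit.

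*Protocol*

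**What the plan says.** The protocol fixes the chemistry panel in section 10.1.2.3. The list opens with creatinine, urea, AST and ALT and continues with "gamma glutamyltransferase, alkaline phosphatase, lactate dehydrogenase, total bilirubin, albumin, total protein, sodium, potassium, chloride, glucose, uric acid, calcium, phosphorus, TSH, T3, and T4". SAP section 10.2 gives the same analytes and likewise ends with "phosphorus, thyroid-stimulating hormone, T3, and T4". The schedule of assessments places chemistry, with thyroid, at Screening and at Week 8/ET.

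Incidence of laboratory PCS values is a named safety endpoint (protocol section 11.6). The protocol sets no limits of its own. Section 11.6.1.4 says: "The criteria for PCS laboratory values will be detailed in the SAP". SAP section 10.2 then makes a value PCS "if they meet either the lower-limit or higher-limit PCS criteria listed in Table 10.2–1". Everything labelled PCS in the laboratory output depends on that table: the incidence, the subject listing and the listing of adverse events in those subjects.

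The chemistry block of the table includes rows such as "Cholesterol, total" that the panel does not contain. SAP section 17.0 declares one departure from the protocol, on weight and height z-scores, and states that there are no others.

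**The concern.** The protocol delegates the criteria to one table, and the SAP recognises no other source. If that table was built for a different panel, two things follow. Some rows have no data to fill them. Some collected analytes can never be flagged, however large the on-treatment change.

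The second matters more. Safety is part of the primary objective, and the protocol gives thyroid function particular attention: it is named in the chemistry row of the schedule, and exclusion criterion 17 requires normal T3 and T4 when TSH is abnormal. Yet none of the three thyroid tests has a PCS criterion. The planned shift tables use low, normal and high, so they do not separate a marginal excursion from a marked one. PCS limits exist to make that separation.

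**Working it through.** The check is a comparison of two lists. The documents state no count, so there is no plan figure to reproduce.

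**Inputs.** (a) The chemistry panel in protocol section 10.1.2.3, repeated in SAP section 10.2. (b) The chemistry rows of SAP Table 10.2–1. Synonyms are matched: urea with blood urea nitrogen, phosphorus with phosphate, and alanine and aspartate transferase with the aminotransferases.

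**Step 1, counts.** The panel has 7 analytes from creatinine to LDH and 13 from total bilirubin to T4: 7 + 13 = 20. The table has 20 chemistry rows.

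**Step 2, comparison.**

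| Group | Analytes | Number |
|---|---|---|
| On the panel and in the table | albumin, ALP, ALT, AST, calcium, chloride, creatinine, glucose, phosphorus, potassium, sodium, total bilirubin, total protein, urea | 14 |
| In the table only | bicarbonate, HDL, LDL, magnesium, total cholesterol, triglyceride | 6 |
| On the panel only | GGT, LDH, T3, T4, TSH, uric acid | 6 |

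Both totals close: 14 + 6 = 20 rows and 14 + 6 = 20 analytes. Each mismatch is 6/20 = 30%.

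**Step 3, could rows have been lost in reading the PDF?** This is unlikely. The chemistry rows run in roughly alphabetical order with no visible gap, and the page break inside the table falls in the hematology block.

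**Step 4, units.** SAP section 10.2 reports laboratory values in SI units, and the four lipid rows carry mmol/L. Their cut-offs are in mg/dL: above 200 for total cholesterol, below 40 for HDL, above 130 for LDL, and above 100 or 130 by age band for triglyceride. The SAP states no conversion.

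**Step 5, consequence under the SAP's rule.** The PCS percentage takes subjects with a non-PCS baseline and at least one post-baseline assessment as the denominator, and those with a PCS post-baseline value as the numerator. For an analyte with no limit, no value can be PCS. The percentage is then either not produced or zero by construction, and no subject enters the two linked listings because of that analyte.

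**Step 6, what still covers the six analytes.** Descriptive statistics and change from baseline (SAP section 10.2), shift tables (SAP section 10.2), full data listings (SAP section 16.3), investigator assessment of clinical significance (protocol section 10.1.2.3), and adverse event reporting where an abnormal result qualifies (protocol section 10.1.2.2).

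**The case against.** The strongest reply is that the table is selective by design. The protocol does not require a limit for every analyte. The same table also omits red cell count, MCV, MCH and MCHC, and urine pH, ketones, blood and microscopy. Omission alone therefore does not prove an error, and that stands. It does not explain the six chemistry rows for tests on neither panel, and the SAP nowhere says that the six omitted chemistry analytes were left out on purpose.

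A reader might infer that the laboratory PCS endpoint cannot be produced. The documents do not support this: it can be produced for every listed analyte that has a limit, including 14 of the 20 in chemistry. A reader might also infer that a marked thyroid or GGT change would go unseen. It would not, because the outputs in Step 6 would show it. What is lost is the PCS flag and its linked listings.

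It is also tempting to say that bicarbonate, magnesium and the lipids are never measured. The documents show only that they are on neither listed panel; the Laboratory Manual is not available. If they are not collected, the extra rows are empty, no result changes and the unit mismatch has no effect.

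Finally, data on the six analytes will not be complete in every subject. Remote visits omit laboratory tests, and Visit 7 results more than one week late are treated as missing for analysis.

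**Conclusion.** The mismatch is real and exact: 6 of 20 chemistry rows have no listed analyte behind them, and 6 of 20 listed analytes have no PCS limit. Neither document offers a fallback or an explanation. Followed to the letter, the SAP gives six rows with no specified data source, and no PCS flag for GGT, LDH, uric acid, TSH, T3 or T4 in a named safety endpoint.

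The effect is limited to descriptive safety output. The conclusion assumes that the two printed panels are the complete list of chemistry tests and that the table is reproduced in full. It does not establish that the omission was unintended, and the documents give no basis for any particular cut-off for the six analytes. This is a minor point, worth correcting because it is cheap and concerns safety reporting in children.

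**What to change.** Before unblinding, reconcile SAP Table 10.2–1 with the chemistry panel:

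- Delete the rows for bicarbonate, magnesium, total cholesterol, HDL, LDL and triglyceride. If those analytes are in fact collected, add them to the listed panel and put the lipid cut-offs in the stated unit.
- Add PCS limits for TSH, T3 and T4 first, then GGT, LDH and uric acid. The sponsor's medical and statistical team should set the values relative to the central-laboratory range. Existing rows use absolute values for some tests and differing multiples of the range for others, so no rule can simply be carried over.
- Name any analyte deliberately left out of the PCS endpoint, including the hematology and urinalysis tests without a limit.

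No new samples are needed. The cost is a table edit, minor programming and a few more PCS flags to review. Timing matters because limits chosen after treatment codes are known are open to challenge.

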10.1.2.3.1 Other Laboratory Variables

Screening for pregnancy using serum β -HCG will be performed at the Screening Visit. Urine pregnancy tests will be performed at the Baseline Visit and the Week 8/End of Treatment Visit (Visit 7).

Urine drug screen (alcohol, opioids, benzodiazepines, tetrahydrocannabinol, barbiturates, amphetamines) will be performed at the Screening Visit and the Week 8/End of Treatment Visit (Visit 7).

Screening for HBsAg, HCVab, and HIV will be performed at the Screening Visit only.

10.1.2.4 Vital Signs

Vital signs (blood pressure, pulse rate, temperature, and respiration rate) will be recorded in a standardized manner (ie, after the subject has rested in the sitting position for 5 minutes). Height, weight, and BMI will also be recorded at specified visits. The times of assessment are outlined in the Schedule of Assessments in [Section 8.1.2](#).

10.1.2.5 Physical Examination

A complete physical examination (including neurological examination) will be performed at the Screening Visit (Visit 1) and at the end of Week 8/ET (Visit 7) by a professionally trained physician or health professional listed on Form FDA 1572 and licensed to perform physical examinations. Any untoward clinically relevant changes will be recorded as AEs.

CONFIDENTIAL

10.1.2.6 Electrocardiogram

A 12-lead single trace ECG will be performed at the times outlined in the Schedule of Assessments in [Section 8.1.2](#) in a standardized manner (ie, after the subject has rested in the semi-supine position for at least 5 minutes). Measurements will include ventricular heart rate, RR interval, PR interval, QRS interval, QT interval, and QTc interval. The QTc interval will be calculated using both the Bazett correction ($QTcB = QT/(RR)^{1/2}$) and the Fridericia correction ($QTcF = QT/(RR)^{1/3}$).

The ECGs will be centrally read. The date and an overall interpretation of the ECG will be recorded in the eCRF. Any abnormalities will be assessed as clinically significant or not clinically significant and recorded on the eCRF.

10.1.3 Pharmacokinetic Assessments

10.1.3.1 Study Drug Concentration Measurements

PK blood samples for measurement of escitalopram and S-demethylcitalopram plasma concentrations will be collected from assented/consented subjects at Visit 5 (Week 4) and Visit 7 (Week 8). For subjects who cannot go to the site for scheduled visits due to the COVID-19 pandemic, PK sample collection can occur at the times specified in [Section 8.2.2.1, Table 1](#). Two PK blood samples per subject will be collected at each of these visits at the following times:

Visit 5:

- For subjects receiving dose in the morning, at 0 hour (predose) and ≥ 1 hour postdose
- For subjects receiving dose in the evening, 2 samples at random times during the visit (ie, postdose from the dose received the previous evening), collected at least 2 hours apart from each other

Visit 7:

- For subjects receiving dose in the morning or in the evening, 2 samples at random times during the visit (ie, postdose from the dose received in the morning or the previous evening), collected at least 2 hours apart from each other

To allow for a predose sampling, subjects on a morning dosing schedule should be instructed to withhold their daily dose on the morning of Visit 5 and take study drug when instructed at the study center.

CONFIDENTIAL

The actual date and clock times of the dose on the PK sampling date as well as the 2 doses taken prior to the PK sampling date, and the actual date and clock times of all blood draws, will be recorded in the eCRF. Blood samples will be collected in prechilled 6 mL Vacutainer® tubes containing lithium heparin as an anticoagulant and processed, stored, and shipped as specified in the Laboratory Manual.

Drug concentration information that may unblind the study will not be reported to investigative sites or blinded personnel until the study has been unblinded. Bioanalytical representatives will be unblinded for PK sample bioanalysis during the conduct of the study. The unblinding of bioanalytical representatives will be carried out in a secure manner following the sponsor's standard operating procedures. Extreme care and diligence will be taken to ensure no other individuals outside the bioanalytical team will be unblinded.

